2.1.2.9 Scheduled study visit and window for the analysis

In order to summarize longitudinal data per time point, assessments will be allocated to visits using predefined time windows. Unless otherwise specified, when more than one assessment is available for a visit, all assessments will be listed under the visit while only the assessment closest to the planned day for the visit will be used for summaries and analyses.

Time windows are provided in Table 2-1.

Assessment	Visit	Time Window	Planned Visit Timing	Time Window Definition
Efficacy Assessm	nents		-	
Tumor response for imaging assessments	Screening	Baseline	Pre- treatment	D-42 to D-1 for whole body bone scans D-21 to D-1 for all other image scans
	C1D28	Between week 3 and week 4 ± 3 days	C1D28	D18 to D31
	C2D28 C4D28	C2D28 ± 7 days C4D28 ± 7 days	D56 D112	D49 to D63 D105 to D119
	every 8 v	,	ease progressio	n, i.e. C6D28, C8D28
	EOT	EOT + 14 days± 3 days		
Biomarkers				
Tumor Biopsy Sam	ples			
Fresh tumor biopsy	Screening	Baseline	Pre- treatment	D-14 to D-1
	C1D8 or	C1D8 ± 3 days or	D8 or	D5 to D11 or
	C1D16	C1D16 + 5 days± 3 days	D16	D13 to D24
	relapse			
CCI				

C = cycle, D = Day, 01 = start of study treatment

All other assessments (i.e. laboratory evaluations etc.) the reported visit will be used

Assessment	Visit	Time Window	PK assessment time point	Time Window Definition
Phase lb (Dose	C1D1	-03:00	< 00:00 pre-dose	C1D1, [-03:00, 00:00]
escalation)	C1D1	± 00:05	00:30 post-dose	C1D1, [00:25, 00:35]
	C1D1	± 00:15	01:30 post-dose	C1D1, [01:15, 01:45]
	C1D1	± 00:30	02:30 post-dose	C1D1, [02:00, 03:00]
	C1D1	± 00:30	04:00 post-dose	C1D1, [03:30, 04:30]
	C1D1	± 01:00	06:00 post-dose	C1D1, [05:00, 07:00]
	C1D1	± 01:00	08:00 post-dose	C1D1, [07:00, 09:00]
	C1D2	-03:00	< 00:00 pre-dose	C1D2, [-03:00, 00:00]
	C1D15	-03:00	< 00:00 pre-dose	C1D15, [-03:00, 00:00]
	C1D15	± 00:05	00:30 post-dose	C1D15, [0:25, 00:35]
	C1D15	± 00:15	01:30 post-dose	C1D15, [01:15, 01:45]
	C1D15	± 00:30	02:30 post-dose	C1D15, [02:00, 03:00]
	C1D15	± 00:30	04:00 post-dose	C1D15, [03:30, 04:30]
	C1D15	± 01:00	06:00 post-dose	C1D15, [05:00, 07:00]
	C1D15	± 01:00	08:00 post-dose	C1D15, [07:00, 09:00]
	C1D16	-03:00	< 00:00 pre-dose	C1D16, [-03:00, 00:00]
	C2D1	-03:00	< 00:00 pre-dose	C2D1, [-03:00, 0:00]
	every c	ycle Day 1 (pre	e-dose), up to Cycle 10 C10D1), i.e. C3D1, C4D1,,
Phase II arm 2 +	C1D1	-03:00	< 00:00 pre-dose	C1D1, [-3:00, 000:00]
Phase II arm 3	C1D1	± 00:05	00:30 post-dose	C1D1, [0:25, 000:35]

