2.1.2.10 Imputation rule of partial or missing dates/data

Imputation rule of partial or missing dates

The following rule will be applied to handle partial dates. When the day is missing, it is imputed to the 15th of the month (e.g., DEC2007 imputed to 15DEC2007). When the day and month are both missing then the date is imputed to July 1st of that year (e.g., 2007 imputed to 01JUL2007). All imputed data are flagged in the listings. Rules for imputing dates for adverse events (AEs), concomitant medications, and anti-neoplastic therapies are described separately in this section.

For computation of time intervals (e.g. elapse time between initial diagnosis to first recurrence/relapse), time interval should be set to missing when the imputation rule leads to a negative value.

As of the date of data cutoff for the purposes of reporting, continuing events (e.g. adverse events, concomitant medication, etc.) will be summarized using the cut-off date as the date of completion, with an indication within listings that the event is continuing.

For patients who discontinue the study with ongoing events, the discontinuation date will be used as the completion date of the event with the appropriate censoring.

Handling of missing data

Unless otherwise specified missing data will not be imputed. Handling of missing data will depend on the nature of the data:

- Baseline characteristics: number of patient with missing data will be reported and descriptive statistics will be computed on patients with non-missing data.
- RECIST best overall response (BOR): patients with missing or unknown BOR will be considered as failure in the overall response rate computation (see Section 3.5.1.1)
- Time-to-event endpoints: appropriate statistical methods will be used to account for censored patients (see Section 3.5.1.2)
- PK and biomarker data, laboratory data, ECG data, vital signs: number of patient with missing data will be reported and descriptive statistics will be computed on patients with non-missing data.

Missing data will simply be noted as missing on appropriate tables/listings.

AE data imputation

Missing and partial date for AE will be handled according to rules specified below.

There will be no attempt to impute the following:

• Completely Missing AE start dates

• AE start dates missing the year.

For partial AE start date, the date imputation will be based on the temporal relation between the partial date and start of treatment date.

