For partial AE end date or completely missing end date (AE is ongoing), the date imputation will be based on the temporal relation between the partial date, the last contact date and the 30-day follow date. If the minimum date of the last contact date and 30-day FU date is before the AE start date (imputed or not), the imputed AE end date will be set to the AE start date.

Table 4-11 provides examples of the different considered imputations for AE start date.

Table 4-12 provides examples of the different considered imputations for AE end date.

AE start date imputation example scenarios

Partial AE start date	Treatment start date	Temporal relationship compared to treatment start	Imputed Date	
12mmyyyy	20OCT2001	Uncertain	<blank></blank>	
ddmmm2000	20OCT2001	Before	01JUL2000	
ddmmm2002	20OCT2001	After	01JAN2002	
ddmmm2001	20OCT2001	Uncertain	210CT2001	
ddSEP2001	20OCT2001	Before	15SEP2001	
ddOCT2001	20OCT2001	Uncertain	210CT2001	
ddNOV2001	20OCT2001	After	01NOV2001	
Table 2-4 AE end date imputation example scenarios				
Partial AE end date	Minimum (Last contact date, 30- day FU date)	Ongoing	Imputed Date	

Concomitant medication date imputation

200CT2001

200CT2001

200CT2001

200CT2001

200CT2001

200CT2001

20OCT2001

20OCT2001

Version 2.2

Missing

ddmmm2000

ddmmm2002

ddmmm2001

ddmmm2001

ddSEP2001

ddOCT2001

ddOCT2001

Table 2-3

Yes

No

No

No

Yes

No

No

Yes

200CT2001

31DEC2000

31DEC2002

31DEC2001

200CT2001

30SEP2001

310CT2001

200CT2001

The imputation of the start date and end data of concomitant medication will follow the same conventions as for AE start date and end date.

Incomplete date for anti-neoplastic therapies

Prior therapies

Start date:

The same rule which is applied to the imputation of AE/concomitant medication start date.

End date:

Imputed date = min (treatment start date -1, last day of the month), if day is missing;

Imputed date = min (treatment start date -1, 31DEC), if month and day are missing.

Date of progression:

Imputed date = min (treatment start date -1, last day of the month), if day is missing;

Imputed date = min (treatment start date -1, 31DEC), if month and day are missing.

If the end date or the date of progression is not missing and the imputed start date is after the end date or after the date of progression, use the min(end date, date of progression) as the imputed start date.

Post therapies

Start date:

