Imputed date = max (last date of study drug + 1, first day of the month), if day is missing;

Imputed date = max (last date of study drug + 1, 01JAN), if day and month are missing.

End date: No imputation.

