3.5.1.1 Best overall response and other binary endpoints

Best overall response

The Best overall response (BOR) is the best response recorded from the start of the treatment until disease progression/recurrence.

Only overall tumor assessments reported by investigator and performed before the start of any further anti-neoplastic therapies (i.e., any additional secondary anti-neoplastic therapy or surgery) will be considered in the assessment of best overall response.

Confirmation of complete and partial responses (CR and PR, respectively) must be made at least 4 weeks apart. Stable disease must occur > 6 weeks after the start of treatment.

Version 2.2

Confidential

Patients who are of unknown clinical response will be treated as non-responders.

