3.5.1.2 Computation of time to event endpoints

Overall survival

Overall survival (OS) is defined as the time from start of treatment to date of death due to any cause. If a patient is not known to have died, survival will be censored at the date of last contact.

As of protocol amendment 10, survival follow-up is no longer performed for patients who have discontinued study treatment in the Phase II part of the study.

Progression free survival

Progression-free survival (PFS) is defined as the time from the date of first study treatment intake to the date of the first documented disease progression or death due to any cause.

By default, if disease progression or death is documented after one single missing tumor evaluation, the actual event date of disease progression/death will be used for the PFS event date. If disease progression or death is documented after two or more missing tumor evaluations, the PFS time of these patients will be censored at the date of the last tumor evaluation with overall lesion response of CR, PR or SD. Patients who begin a new antineoplastic therapy prior to disease progression or death will be censored at the last adequate tumor evaluation prior to the start of the new antineoplastic therapy.

As of protocol amendment 10, post-treatment disease progression follow-up is no longer performed for patients who have discontinued study treatment in the Phase II part of the study.

Time to (overall) response

Time to (overall) response (TTR) will be based on "responders" only and is the time between the date of first treatment administration and the first documented response (CR or PR).

Duration of overall response

Duration of overall response (DOR) will be based on "responders" only and is the time between the date of first documented response (CR or PR) and the date of first documented progression or death due to underlying cancer. If progression or death due to underlying cancer has not occurred, then the patient is censored at the date of last adequate tumor assessment.

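### The imputation rule for partial post-study anticancer therapy dates ignores a documented progression, so a progression first seen after the last dose can be turned into a PFS censoring

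*SAP*

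**What the plan says.** SAP section 2.1.2.10 has a separate rule for incomplete anticancer therapy dates. For therapy after study treatment with the day missing, it reads "Imputed date = max (last date of study drug + 1, first day of the month), if day is missing". With day and month missing, it reads "Imputed date = max (last date of study drug + 1, 01JAN), if day and month are missing". The general mid-month rule ("When the day is missing, it is imputed to the 15th of the month") does not apply, because that section handles anticancer therapies separately. For prior therapies, the same section does check the imputed start against progression: if the imputed start falls too late, the instruction is to "use the min(end date, date of progression) as the imputed start date". Post-study therapy has no counterpart.

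The date feeds two derivations. For PFS, section 3.5.1.2 states: "Patients who begin a new antineoplastic therapy prior to disease progression or death will be censored at the last adequate tumor evaluation" before that therapy. For best overall response, section 3.5.1.1 counts only assessments "performed before the start of any further anti-neoplastic therapies".

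Table 2-1 in section 2.1.2.9 gives the end-of-treatment tumor assessment window as "EOT + 14 days± 3 days", without resolving it into days.

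**The concern.** The rule gives the earliest date compatible with the recorded month or year and with having stopped study drug. Its only lower limit is the day after the last dose. If the first progression is found at a scan after the last dose and the patient then switches therapy, the imputed start can fall before a progression that in truth came first. The PFS rule then discards an observed event and censors the patient at an earlier scan.

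This would happen selectively, in patients who came off drug, progressed and moved on quickly. The censoring is informative and flatters the Kaplan-Meier curve. PFS is planned for the final report for both combinations (Tables 14.2.3.1b and 14.2.3.1d, with the matching figures).

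**Working it through.** The SAP states no figure on this point, so there is nothing to reproduce. I applied the printed rules literally.

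**Condition for losing the event.** Let L be the last dose date, P the first documented progression, T the true start of new therapy (T > P), and F the first day of the recorded month, or 1 January of the recorded year. The imputed start is max(L + 1, F). The event is lost when the imputed start is before P, that is, when P ≥ L + 2 and F < P.

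**Worked cases, day missing.**

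| Last dose | Progression | True start | Imputed start | PFS |
|---|---|---|---|---|
| 10 Mar | 24 Mar | 28 Mar | max(11 Mar, 1 Mar) = 11 Mar | event lost |
| 20 Mar | 3 Apr | 10 Apr | max(21 Mar, 1 Apr) = 1 Apr | event lost |
| 10 Mar | 24 Mar | 4 Apr | max(11 Mar, 1 Apr) = 1 Apr | event kept |
| 24 Mar | 24 Mar | 28 Mar | max(25 Mar, 1 Mar) = 25 Mar | event kept |

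The mid-month rule would not rescue the first case: 15 March is still before 24 March.

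**The scan window.** The entry for the end-of-treatment scan can be read two ways. Taken as a target of day +14 with a tolerance of 3 days, it gives +11 to +17. But the fresh-biopsy row of the same table uses the same form ("C1D16 + 5 days± 3 days") and resolves it as D13 to D24, that is, 3 days before the target to 5 + 3 = 8 days after it. Read like that, the end-of-treatment window is −3 to +17 days.

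**Share of events lost.** I took every last-dose day over three calendar years, every scan day in the window, and fixed gaps from progression to true therapy start. The gaps are assumptions, and the end-of-treatment date is taken as the last-dose date. Combinations with therapy starting on or before the last dose were dropped.

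| Gap from progression to therapy | Day missing, +11 to +17 | Day missing, −3 to +17 |
|---|---|---|
| 3 days | 86.8% | 69.5% |
| 7 days | 73.7% | 56.2% |
| 14 days | 50.7% | 38.6% |
| 21 days | 27.7% | 21.1% |
| 28 days | 4.9% | 3.8% |

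With only the year recorded, the shares over the same gaps are 92–99% for the first window and 70–79% for the second. For scans on or before the last dose the share is 0%.

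**Effect of one lost event on the curve.** Suppose n patients are at risk just after the earlier scan and m others have events before P, with no other censoring. Keeping the event multiplies the curve by (n − m − 1)/n up to and including P. Censoring the patient at the earlier scan instead gives (n − 1 − m)/(n − 1). From P onward the curve is therefore too high by the factor n/(n − 1). With an assumed n = 20, that is 20/19 = 1.053.

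**With the fix.** Adding P + 1 to the maximum when P lies in the recorded period gives no lost events in any enumerated combination. The first worked case becomes 25 March and the event on 24 March is kept.

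**The case against.** The strongest reply is that the existing floor already protects the usual case. Patients are treated until progression, so a progression at a scheduled on-treatment scan is normally dated on or before the last dose. The imputed start cannot be earlier than the day after that dose, so the event survives. This stands. Exposure requires drug stopped before progression was documented, a first progression at least two days after the last dose, a partial therapy date, and a recorded period that begins before the progression.

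A reader might infer that progressions found at the end-of-treatment scan generally become censorings. The documents do not support that. The scan window is ambiguous, and under the wider reading some of these scans fall on or before the last dose and are safe.

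A reader might also project a loss of 5% to 20% of all progression events and a matching rise in 12-month PFS. The SAP gives no input for this. At a lost share of 66%, losing 20% of all progressions would need 0.20/0.66 = 30% of them to be both first seen after the last dose and followed by a partially dated therapy. If, purely as an illustration, 20% were seen after the last dose and 20% of therapy dates were partial, lost shares of 50% to 66% would give 0.20 × 0.20 × 0.50 = 2.0% to 0.20 × 0.20 × 0.66 = 2.6%.

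A third tempting inference is that the response rate is harmed too. It is not in this scenario. Best overall response runs only up to progression, so dropping a later progression scan removes no earlier response. If that scan was the only one, the patient is unknown instead of progressed and still counts as a non-responder.

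Finally, PFS is a secondary endpoint analysed descriptively, with no hypothesis test, and imputed dates are flagged in the listings. That limits the consequence but does not correct the curve.

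**Conclusion.** The concern holds as a limited one. Applied as written, the rules can replace an observed progression with an earlier censoring, and nothing in the SAP gives a documented progression precedence over an imputed therapy date. The bias in PFS is upward from the date of the lost progression.

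Among exposed cases with the day missing, about 4% to 87% lose the event. That range rests on assumed gaps of 3 to 28 days, on the two readings of the scan window, and on the end-of-treatment date being the last-dose date. The number of exposed patients cannot be determined from the SAP and is probably small, so no overall shift in PFS can be stated. No test, sample size or response rate is affected. The correction is cheap enough to be worth making.

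**What to change.** For PFS only, define the imputed start of post-study anticancer therapy as the latest of:

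- the last date of study treatment (latest component) + 1;
- the first day of the recorded month, or 1 January of the recorded year;
- the date of first documented progression + 1, when that progression falls in the recorded month or year.

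Alternatively, state in section 3.5.1.2 that a documented progression takes precedence over an imputed therapy date. Fully dated switches before progression stay censored as now.

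Leave the best overall response rule on the present imputed date. Moving the imputed start past any scan in the recorded period could credit a response seen after a real switch to study treatment.

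The cost is one line of text and one derivation. The downside is small: a progression that truly followed a switch within the same partially dated period would be kept as an event.

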2.2 Analysis sets

For inclusion in any analysis set it is required that a patient has correctly consented and has received at least one dose of study treatment. For those incorrectly consented patients, they will be excluded from all analysis.

The following analysis sets which will be derived prior to database lock will be used.

Full Analysis Set

The FAS includes all patients who received at least one dose of LGX818 or MEK162 or LEE011. Patients will be classified according to the planned treatment regimen (dose, schedule, tablet variant). The FAS will be used for all listings of raw data. Unless otherwise specified the FAS will be the default analysis set used for all analyses.

Note that patients who were screened and are eligible but never started treatment will not be included in the FAS. This is considered as an acceptable deviation from the ITT principle in the context of the Phase I study in which safety is considered as a primary objective.

The FAS will be used for all listings of raw data. Unless otherwise specified the FAS will be the default analysis set used for all analyses. Patients will be analyzed according to the planned treatment regimen.

Safety Set

The safety set includes all patients who received at least one dose of LGX818 or MEK162 or LEE011, and have at least one valid post-baseline safety assessment. The statement that a patient had no AEs (on the AE eCRF) constitutes a valid safety assessment.

Patients will be classified according to treatment received (See Section 2.1.1.2).

Dose Determining Set (DDS)

The dose-determining set (DDS) includes all Phase Ib patients from the safety set who either completed a minimum exposure requirement and have sufficient safety evaluations or discontinued prematurely due to a dose limiting toxicity (DLT).

A patient is considered to have met the minimum exposure requirement if having received at least 75% of the planned combination doses (i.e. 21 out of 28 planned daily doses for QD or BID, 11 out of 14 planned doses for an every other day dosing schedule, and 16 days out of 21 days for 3 week on, 1 week off dosing schedule) of study treatment within the first Cycle of dosing. The length of a cycle is 28 days.

Patients who do not experience DLT during the first cycle will be considered to have sufficient safety evaluations if they have been observed for ≥ 28 days following the first dose, and are considered by both the Sponsor and Investigators to have enough safety data to conclude that a DLT did not occur.

Patients excluded from this analysis set will be identified through a manual protocol deviation (PD) with severity code 18 ("exclude from MTD determining analysis set")

Below is a summary of protocol deviations leading to exclusion from analysis sets. Severity codes are defined in the Novartis Validation and Analysis Planning (VAP) Module 3. This study was previously under the sponsorship of Novartis and transitioned to Pfizer sponsorship with PPD oversite, but protocol deviations are still coded according to the Novartis VAP Module 3. Patients were excluded from the analysis sets defined above based on the protocol deviations entered in the database.

Analysis set	Protocol deviations [severity codes leading to exclusion]		
Full analysis set	Patient not correctly consented [8]		
Safety set	Patient not correctly consented [8]		
	Patient has no adverse event record (including no record that no event occurred) [5]		
Dose determining set	Patient not correctly consented [8]		
	Patient did not have sufficient safety evaluations for the investigator to be able to complete the end of cycle 1 DLT		

assessment and did not have a DLT [18]
Minimum exposure requirements not met and did not have a DLT [18]

[8] (exclude from all analysis) / [5] (exclude from all safety analyses) / [18] (exclude from MTD determining analysis set)

2.3 Interim analyses

Since Phase II Arm 1 was terminated before the planned number of patients was reached, this part of the analysis will not be conducted.

3 Statistical methods used in reporting

The data will be summarized by treatment group and overall (when appropriate) with respect to demographic and baseline characteristics, preliminary efficacy and safety observations and measurements, and all relevant PK and PD measurements using descriptive statistics (quantitative data) and contingency tables (qualitative data).

Categorical data will be presented as frequencies and percentages. For continuous data, mean, standard deviation, median, 25th and 75th percentiles, minimum and maximum will be presented.

Data from participating centers will be combined. Unless otherwise specified, patients of the escalation part treated at the MTD with the same dose level but were recruited at different point in the study will be pooled into a single treatment group.

Listings of all raw data will be produced and ordered by treatment group (in Phase Ib) or patient group (in Phase II), center, country and patient. Unless otherwise specified, if multiple measurements are available for one time point (or period), an average will be provided to represent the time point (or time period). Unless specified otherwise, all percentage is with respect to big N.

